## Table 6: Power for Prospective Study- General Population –Diabetes End Point, Alpha = .01, N = 7013, 5 Years Accrual, Follow-Up to age 15, 4% Conversion among Unexposed at 15 Years

Exposed %	LTFU %/year	Power ( HR = 1.5)	Power ( HR = 2.0 )
1	0	0.05	0.21
5	0	0.26	0.89
10	0	0.52	0.99
20	0	0.81	0.99
1	2	0.04	0.17
5	2	0.21	0.82
10	2	0.44	0.98
20	2	0.72	0.99
1	5	0.03	0.13
5	5	0.16	0.71
10	5	0.34	0.95
20	5	0.59	0.99
1	10	0.03	0.09
10	10	0.23	0.83
20	10	0.42	0.98
5 10	10 10	0.11 0.23	0.52 0.83

Table 7: Power for Prospective Study- Relatives – Diabetes End Point Alpha = .01, N = 788, 5 Years Accrual, Follow-Up to age 15, 13.3% Conversion among Unexposed at 15 Years

Exposed %	LTFU %/year	Power (HR = 1.5)	Power ( HR = 2.0)
1	0	0.02	0.06
5	0	0.07	0.33
10	0	0.14	0.62
20	0	0.27	0.87
1	2	0.02	0.05
5	2	0.06	0.27
10	2	0.12	0.53
20	2	0.22	0.80
1	5	0.02	0.04
5	5	0.05	0.21
10	5	0.09	0.42
20	5	0.17	0.68
1	10	0.02	0.03
5			0.03
	10	0.04	
10	10	0.06	0.29
20	10	0.11	0.51

Table 8: Power for Prospective Study- Pooled Sample – Diabetes End Point,
Alpha = $.01$ , N = 7801, 5 Years Accrual, Follow-Up to age 15,
5.5% Conversion among Unexposed at 15 Years

$\begin{array}{c ccccccccccccccccccccccccccccccccccc$	Exposed %	LTFU %/year	Power ( HR = 1.5)	Power ( HR = 2.0 )
$ \begin{array}{c ccccccccccccccccccccccccccccccccccc$				
$\begin{array}{c ccccccccccccccccccccccccccccccccccc$	1	0	0.07	0.35
$\begin{array}{c ccccccccccccccccccccccccccccccccccc$	5	0	0.43	0.98
$\begin{array}{c ccccccccccccccccccccccccccccccccccc$	10	0	0.75	0.99
$ \begin{array}{cccccccccccccccccccccccccccccccccccc$	20	0	0.95	0.99
$\begin{array}{c ccccccccccccccccccccccccccccccccccc$	1	2	0.06	0.29
$\begin{array}{c ccccccccccccccccccccccccccccccccccc$	5	2	0.35	0.96
$\begin{array}{c ccccccccccccccccccccccccccccccccccc$	10	2	0.66	0.99
$ \begin{array}{cccccccccccccccccccccccccccccccccccc$	20	2	0.91	0.99
$ \begin{array}{cccccccccccccccccccccccccccccccccccc$				
$\begin{array}{cccccccccccccccccccccccccccccccccccc$		5	0.05	0.22
20         5         0.82         0.99           1         10         0.04         0.14           5         10         0.18         0.75           10         10         0.37         0.96	5	5	0.27	0.90
1         10         0.04         0.14           5         10         0.18         0.75           10         10         0.37         0.96	10		0.54	0.99
5100.180.7510100.370.96	20	5	0.82	0.99
5100.180.7510100.370.96	1	10	0.04	0.14
10 10 0.37 0.96				

Table 9: Power for Prospective Study – General Population – Autoantibodies End Point, Alpha = .01, N = 7013, 5 Years Accrual, Follow-Up to age 15, 4% Conversion among Unexposed at 6 Years

$\begin{array}{cccccccccccccccccccccccccccccccccccc$	
5 0 0.66 0.99	
10 0 0.93 0.99	
10 0.00	
20 0 0.99 0.99	
1 2 0.10 0.47	
5 2 0.57 0.99	
10 2 0.88 0.99	
20 2 0.99 0.99	
1 5 0.07 0.36	
5 5 0.45 0.99	
10 5 0.78 0.99	
20 5 0.96 0.99	
1 10 0.05 0.25	
5 10 0.31 0.93	
10 10 0.60 0.99	
20 10 0.87 0.99	

Table 10: Power for Prospective Study –Relatives – Autoantibodies End Point,
Alpha = $.01$ , N = 788, 5 Years Accrual, Follow-Up to age 15,
13.3% Conversion among Unexposed at 6 Years

Exposed %	LTFU %/year	Power ( HR = 1.5)	Power ( HR = 2.0)
1	0	0.03	0.12
5	0	0.16	0.67
10	0	0.34	0.94
20	0	0.61	0.99
1	2	0.03	0.10
5	$\frac{2}{2}$	0.03	0.10
10	2	0.29	0.89
20	2	0.52	0.99
1	5	0.03	0.08
5	5	0.11	0.48
10	5	0.22	0.80
20	5	0.42	0.97
1	10	0.02	0.06
5	10	0.08	0.35
10	10	0.15	0.65
20	10	0.29	0.89

Table 11: Power for Prospective Study – Pooled Sample – Autoantibodies End Point Alpha = .01, N = 7801, 5 Years Accrual, Follow-Up to age 15, 5.5% Conversion among Unexposed at 6 Years

Exposed %	LTFU %/year	Power ( HR = 1.5)	Power (HR = 2.0)
1	0	0.15	0.68
5	0	0.78	0.99
10	0	0.98	0.99
20	0	0.99	0.99
1	2	0.12	0.56
5	2	0.67	0.99
10	2	0.94	0.99
20	2	0.99	0.99
1	5	0.12	0.56
5	5	0.67	0.99
10	5	0.94	0.99
20	5	0.99	0.99
1	10	0.08	0.40
5	10	0.49	0.99
10	10	0.82	0.99
20	10	0.98	0.99

Table 12: Interim Analysis Power for Prospective Study- General Population –Diabetes End Point, Alpha = .01, N = 7013, 5 Years Accrual, Follow-Up to age 5, 1.4% Conversion among Unexposed at 5 Years

Exposed %	LTFU %/year	Power ( HR = 2.0)	Power (HR = 3.0)	Power $(Hr = 5.0)$
1	0	0.08	0.42	0.98
5	0	0.50	0.99	0.99
10	0	0.81	0.99	0.99
20	0	0.97	0.99	0.99
1	2	0.08	0.39	0.97
5	2	0.46	0.99	0.99
10	2	0.78	0.99	0.99
20	2	0.95	0.99	0.99
1	5	0.07	0.34	0.95
5	5	0.41	0.98	0.99
10	5	0.72	0.99	0.99
20	5	0.93	0.99	0.99
1	10	0.06	0.28	0.91
5	10	0.34	0.95	0.99
10	10	0.63	0.99	0.99
20	10	0.87	0.99	0.99

Table 13: Interim Analysis Power for Prospective Study- General Population –Diabetes End Point, Alpha = .01, N = 7013, 5 Years Accrual, Follow-Up to age 10, 2.7% Conversion among Unexposed at 10 Years

Exposed %	LTFU %/year	Power ( HR = 2.0)	Power (HR = 3.0)	Power ( HR = 5.0)
1	0	0.14	0.66	0.99
5	0	0.75	0.99	0.99
10	0	0.96	0.99	0.99
20	0	0.99	0.99	0.99
1	2	0.12	0.59	0.99
5	2	0.69	0.99	0.99
10	2	0.94	0.99	0.99
20	2	0.99	0.99	0.99
1	5	0.10	0.50	0.99
5	5	0.59	0.99	0.99
10	5	0.89	0.99	0.99
20	5	0.99	0.99	0.99
1	10	0.08	0.38	0.97
5	10	0.46	0.99	0.99
10	10	0.77	0.99	0.99
20	10	0.95	0.99	0.99

The above tables demonstrate that a trigger will have to be associated with a hazard ratio of about 2.0 in order for us to have reasonable power. In that case, we will have adequate power for exposure rates of at least 5% if we have little (not exceeding 2% per year) loss to follow-up. If we have more losses to follow-up, we will need to have at least a 10% exposure rate for a trigger with a hazard ratio of 2.0.

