## 5. Hypothesis

- 1. Initiation of persistent beta-cell autoimmunity and progression from beta-cell autoimmunity to diabetes is increased with:
  - a. Exposure to a trigger factor during pregnancy, such as infections, preeclampsia, blood incompatibility, or birth weight.
  - b. Differences in the timing of the introduction and/or the type of dietary constituents that include exposure to cereals or gluten, exposure to cow's milk during infancy and/or childhood, and short duration of breast-feeding;
  - c. Lower intake of serum 25 hydroxyvitamin D in early infancy, vitamin E, antioxidants (e.g., carotenoids, ascorbic acid, selenium, or omega-3 fatty acids);
  - d. Higher frequency of specific (e.g., enterovirus, rotavirus, or bacterial) infections, or non-specific childhood infections including those that exhibit molecular mimicry;
  - e. Increased exposure to routine childhood immunizations and their timing;
  - f. Environmental factors that may be contained in drinking water (e.g., low concentrations of zinc or high concentrations of nitrates, or lower pH levels);
  - g. Exposure to household pets, and various allergies;
  - h. Excessive weight gain;
  - i. Increased psychological stress.
- 2. The risk of persistent beta-cell autoimmunity is lower in children from the general population than in offspring or siblings of T1DM patients when stratifying for the HLA DR-DQ genotype and exposure to environmental triggers.
- 3. The interaction of HLA DR-DQ genotype with exposure to dietary or infectious factors leads to increased incidence of beta-cell autoimmunity and T1DM.

4. We expect that in some families study participation will be associated with affective (anxiety, depression) and behavioral responses (e.g. actions to prevent possible T1DM).

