## **10.2. Plan and Timeline of Proposed Analyses**

In general the study is designed to have 80% power or greater for detecting hazard ratios of 2 or greater for exposures 10% or greater, based on the expectation of being able to enroll 7,013 subjects from the general population and 788 relatives in five years, with 15 years of post-accrual follow-up. The actual study experience may be different and it is prudent to provisionally plan for interim analyses. In doing so, we consider the following caveats: 1) Laboratory determinations made for interim analysis of stored samples need to be identical to the laboratory methods of the same determinations to be made at the end of the study if the data are to be aggregated, and 2) Some longitudinal testing of stored samples is prudent to ensure sample integrity and quality.

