Ov	er 5 years	General Population	on FDF	ł			
Enroll		7,013	788				
Cases - autoantibodies by age 6		281 (4%)	105 (13.	3%)			
Cases - T1DM by age 15		281 (4%)	105 (13.	3%)			

Based on submissions by the participating institutions, we expect to be able to enroll 7,013 subjects from the general population and 788 relatives in five years. Those from the general population and the relatives are expected to have about 4% and 13.3% autoimmune conversion at 6 years respectively. Tables 6-13 below give the power for a Log Rank Test at a two-sided 0.01 significance level for the general population subjects, the relatives, and the pooled sample accrued over 5 years with 15 years of post-accrual follow-up for dichotomous pre-birth triggers of frequencies 1%, 5%, 10%, and 20% and hazard ratios of 1.5 and 2.0 and losses to follow-up at rates of 0%, 2%, 5%, and 10% per year. These calculations are based on the method of Lakatos (Lakatos, 1998) using a computer program described by Cantor (Cantor, 2003).

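### The prospective power figures are worked out for pre-birth triggers only but stated for any trigger; they do not hold for general-population diabetes at 5% exposure once exposure starts from about 9 months of age

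*Protocol*

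**What the plan says.** Protocol Section 10.3 introduces Tables 6 to 13 as log-rank power "for dichotomous pre-birth triggers of frequencies 1%, 5%, 10%, and 20% and hazard ratios of 1.5 and 2.0". The group is therefore fixed at birth, and the exposed child carries the raised hazard throughout follow-up.

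Two statements draw on this work without repeating the limit:

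- The closing paragraph of Section 10.3, after Table 13, takes a trigger with a hazard ratio of about 2.0 and says: "In that case, we will have adequate power for exposure rates of at least 5% if we have little" loss, defined there as no more than 2% a year. With heavier loss it asks for at least 10% exposure.
- Section 10.2 describes the study in general as having "80% power or greater for detecting hazard ratios of 2 or greater for exposures 10% or greater".

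Of the nine trigger groups in hypothesis 1 of Section 5, only item (a) is set in pregnancy. The other eight act wholly or mainly after birth, although some, such as drinking water or household pets, can be present from birth. Section 10.4.1 sends HLA, diet, psychological distress and clinical events to the prospective analysis. Section 10.6 plans models with time-dependent covariates, and no power figure accompanies them.

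**The concern.** A trigger that starts at age 2 cannot raise the hazard before age 2. If exposure is analysed as time-dependent, the events before onset carry no information on it. If children are grouped as ever or never exposed and compared from birth, those early events also dilute the contrast. In both cases the same percentage exposed buys less power than for a trigger present at birth.

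The tables are used beyond planning. Section 10.2.3 screens further interim hypotheses by the hazard ratio detectable at 80% power, and Section 10.9 refers to the tables to judge the effect of deviations. A null result for a later exposure could therefore be read as adequately powered when it was not.

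**Working it through.** **Inputs (Section 10.3, Table 6).** N = 7,013 from the general population; 4% diabetes by 15 years in the unexposed; hazard ratio 2.0. The tables "give the power for a Log Rank Test at a two-sided 0.01 significance level", with "losses to follow-up at rates of 0%, 2%, 5%, and 10% per year". The method: "These calculations are based on the method of Lakatos". Conversion is taken as exponential, as in Section 10.2.3. Follow-up is 5 years of uniform accrual plus 15 years, as in the text before Table 6. Onset ages are my assumption.

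**Formulas.** Unexposed hazard: −ln(1 − 0.04)/15 = 0.00272 per year. Loss hazard at 2% a year: −ln(0.98) = 0.0202. At each age let p be the exposed share of those at risk, d the expected events and d1 those among the exposed. Sum U = Σ(d1 − p·d) and V = Σ p(1 − p)·d over follow-up. Power = Φ(U/√V − 2.576).

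**The plan's own figures first (onset at birth).**

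| Exposed / loss | Table 6 | Recomputed |
|---|---|---|
| 5% / 0% | 0.89 | 0.890 |
| 5% / 2% | 0.82 | 0.820 |
| 10% / 2% | 0.98 | 0.983 |
| 10% / 5% | 0.95 | 0.944 |

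The basis is therefore the tables' own.

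**Later onset, time-dependent exposure, 5% exposed, 2% loss.** The hazard doubles from the onset age, and the child counts as unexposed until then.

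| Onset | U | V | U/√V | Power |
|---|---|---|---|---|
| Birth | 12.78 | 13.41 | 3.491 | 0.82 |
| 3 months | 12.56 | 13.18 | 3.461 | 0.81 |
| 1 year | 11.92 | 12.50 | 3.370 | 0.79 |
| 2 years | 11.07 | 11.61 | 3.249 | 0.75 |
| 4 years | 9.43 | 9.89 | 2.998 | 0.66 |

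Power passes below 0.80 at an onset age of about 9 months.

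**Same case, fixed ever/never groups compared from birth by log-rank.** U is unchanged, but V stays near 13.4 because children not yet exposed count in the exposed group.

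- 3 months: 12.56/√13.40 = 3.431, power 0.80
- 1 year: 11.92/√13.40 = 3.256, power 0.75
- 2 years: 11.07/√13.39 = 3.026, power 0.67
- 4 years: 9.43/√13.36 = 2.580, power 0.50

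This variant matters because Section 10.1 plans log-rank comparisons of fixed groups for the diet and water factors.

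**10% exposed, general-population diabetes.**

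| Onset | 2% loss, time-dependent | 5% loss, time-dependent | 2% loss, fixed groups | 5% loss, fixed groups |
|---|---|---|---|---|
| Birth | 0.98 | 0.94 | 0.98 | 0.94 |
| 2 years | 0.96 | 0.89 | 0.93 | 0.82 |
| 4 years | 0.93 | 0.81 | 0.82 | 0.62 |
| 6 years | 0.87 | 0.70 | 0.64 | 0.40 |

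With time-dependent exposure, 0.80 is kept for onset up to about 7 years at 2% loss and about 4 years at 5% loss.

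**Other samples and endpoints, 5% exposed, 2% loss, time-dependent.**

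- Pooled diabetes (N = 7,801, 5.5% by 15 years): 0.96 from birth, 0.94 from age 1, 0.92 from age 2, 0.87 from age 4, 0.79 from age 6.
- General-population autoantibodies (4% by 6 years, constant hazard as in Table 9): 0.99 or more for onset up to age 2, 0.98 from age 4, 0.95 from age 6.

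**The case against.** **The limit is stated.** Section 10.3 labels the tables as pre-birth, and the closing paragraph says that it speaks from them. That is fair, but the conclusion is worded for any trigger, and Section 10.2 stands apart from the tables altogether.

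**The loss is small where it matters most.** Cereal or gluten exposure before 3 months, a named prospective analysis, loses 1 to 2 points. This stands, and the fix allows for it.

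**Infections do not rest on these tables.** A reader might cite hypothesis 1(d), "Higher frequency of specific (e.g., enterovirus, rotavirus, or bacterial) infections", as a clear post-birth case. Section 10.5.1 sends viral, bacterial, dietary-biomarker and inflammatory exposures to the nested case-control analysis. Its Tables 14 to 16 use exposure prevalence among controls and assume nothing about birth. This objection stands in full.

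**Autoantibodies.** A reader might count conversions only to age 6 and find a steep fall. Table 9 follows children to age 15 and uses age 6 only to fix the rate. Sections 8.11 and 8.12.1.2 report fewer conversions at ages 10 to 15, not none after 6. The constant hazard is thus on the favourable side, but the documents do not support stopping at 6.

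**Enrolment exceeded the projection.** The Introduction gives 8,677 followed against 7,801. If the general-population share grew alike (an assumption), U/√V rises by √(8,677/7,801) = 1.055. Power at 5% and 2% loss becomes about 0.84, 0.80 and 0.72 for onset at 1, 2 and 4 years. That softens the shortfall but does not remove it, and the printed statements rest on the projected numbers.

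**Conclusion.** The point holds in a limited form. The 5% adequacy statement for general-population diabetes starts from 0.82, two points above 0.80. It falls below 0.80 for onset from about 9 months under time-dependent exposure, to 0.75 at 2 years and 0.66 at 4 years, and lower still with fixed groups. These figures assume the projected numbers, a hazard ratio of 2, constant hazard, the tables' own follow-up and my onset ages.

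A reader might infer that the 80% statement fails for post-birth triggers at large. It does not. At 10% exposure it survives onset through the first years of life, and at 5% exposure so do the pooled diabetes and general-population autoantibody analyses. It fails for late onset, and earlier if fixed groups are compared: at 5% loss it is 0.82 at onset age 2 and 0.62 at 4.

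One separate matter should not be charged to onset age. The Table 6 titles stop follow-up at age 15, but the figures reproduce only with up to 5 further years. With follow-up ending at 15, the 5% / 2% cell is 0.76 even from birth.

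**What to change.** - In Section 10.2 and in the closing paragraph of Section 10.3, limit the power statements to exposures present from birth or early infancy.
- Withdraw the 5% adequacy statement for general-population diabetes when onset is later.
- Add power rows by onset age, for example 1, 2, 4 and 6 years, from the same program. Label each row with the analysis it assumes (time-dependent exposure or fixed groups) and the follow-up used.

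The cost is one extra power run, a few changed sentences, and a less favourable stated power for later exposures. Sample, visits and procedures are unchanged.

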## 4. Objectives

The primary objective of this study is to identify environmental factors that predispose to or protect from beta-cell autoimmunity and T1DM.

The secondary objectives include:

[figure not shown]
- 1. Identification of potential differences in the environmental determinants of T1DM across diverse populations and ethnic groups.
- 2. Identification of potential differences in the environmental determinants of T1DM between children with and without first-degree T1DM relatives.
- 3. Establishment of a central repository for data and biologic samples for subsequent hypothesis based research.
- 4. Exploration of psychosocial corollaries of the ascertainment of risk status for autoimmunity and T1DM in newborns.
- 5. Exploration of gene-environmental interactions.
- 6. Better understanding of the natural history of the disease.

[figure not shown]

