#### **10.3. Sample size and power determination**

Subjects will be recruited over a five-year period and followed until they reach the age of 15 years old. Thus all subjects will have 15 years of follow-up.

#### Table 5

	Screening/y remaining 3 accru	years of	Eligible/year for remaining 3 years of accrual		Enroll/year for remaining 3 years of accrual			rual		
Center	General Population	FDR	Eligibility Rate GP	General Population	Eligibility Rate FDR	FDR	Enrollment Rate GP	General Population	Enrollment Rate FDR	FDR
Colorado	16,316	176	5.1%	832	23.5%	41	42%	350	64%	26
Finland	11,204	132	5.6%	627	35.1%	46	44%	276	60%	28
Georgia/Florida	14,272	172	3.5%	500	16.4%	28	33%	165	50%	14
Germany	7,296	356	3.9%	285	19.5%	69	30%	85	80%	56
Sweden	8,956	220	7.6%	681	18.3%	40	65%	442	65%	26
Washington State	23,628	204	3.9%	921	26.7%	54	37%	341	75%	41
TOTAL:	81,672	1,260		3,846		278		1659		191

	Actual total screened by site for first 2		Projected total screened b	y site for remaining	Total screened by site for 5 years of accrual	
	years of accrual		3 years of a	ccrual		
Center	General Population	FDR	General Population	FDR	General Population	FDR
Colorado	17,896	296	48,948	528	66,844	824
Finland	22,827	271	33,612	396	56,439	667
Georgia/Florida	25,204	226	42,816	516	68,020	742
Germany	6,695	526	21,888	1,068	28,583	1,594
Sweden	17,991	358	26,868	660	44,859	1,018
Washington State	20,363	139	70,884	612	91,247	751
TOTAL:	110,976	1,816	245,016	3,780	355,992	5,596

Actual total eligible by s accru		•	Projected total eligible 3 years of		Total eligible by site accrual	Total eligible by site for 5 years of accrual	
Center	General Population	FDR	General Population	FDR	General Population	FDR	
Colorado	811	66	2,496	123	3,307	189	
Finland	1,254	94	1,881	138	3,135	232	
Georgia/Florida	824	34	1,500	84	2,324	118	
Germany	244	99	855	207	1,099	306	
Sweden	1,282	61	2,043	120	3,325	181	
Washington State	635	28	2,763	162	3,398	190	
TOTAL:	5,050	382	11,538	834	16,588	1,216	
	Actual total enrolled by	site for first 2 years of	Projected total enrolled by site for remaining 3 years of accrual		Total enrolled by site for 5 years of accrual		
	accri	ual					
Center	General Population	FDR	General Population	FDR	General Population	FDR	
Colorado	262	35	1,050	78	1,312	113	
Finland	556	43	828	84	1,384	127	
Georgia/Florida	204	15	495	42	699	57	
Germany	72	69	255	167	327	236	
Sweden	796	40	1,326	78	2,122	118	
Washington State	146	14	1,023	123	1,169	137	
TOTAL:	2,036	216	4,977	572	7,013	788	

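### Section 10.3 concludes that 5% exposures are adequately powered at a hazard ratio of 2.0, but its own tables show this is untrue for the relatives

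*Protocol*

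**What the plan says.** Section 10.3 states that Tables 6 to 13 "give the power for a Log Rank Test at a two-sided 0.01 significance level for the general population subjects, the relatives, and the pooled sample". Two of them, Table 7 (diabetes) and Table 10 (autoantibodies), are for relatives alone. The heading of Table 7 reads "Alpha = .01, N = 788, 5 Years Accrual, Follow-Up to age 15, 13.3% Conversion among Unexposed at 15 Years".

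After Table 13, the closing paragraph of 10.3 draws one conclusion from all the tables above it. A hazard ratio of about 2.0 is needed for reasonable power, and given such a ratio "we will have adequate power for exposure rates of at least 5% if we have little (not exceeding 2% per year) loss to follow-up". With heavier loss, it says, an exposure rate of at least 10% will be needed. It names neither a population nor an end point.

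The yardstick for adequate power is in section 10.2, where the study is said in general to have "80% power or greater for detecting hazard ratios of 2 or greater for exposures 10% or greater". That sentence cites both enrolment targets, 7,013 from the general population and 788 relatives. Secondary objective 2 in section 4 is "Identification of potential differences in the environmental determinants of T1DM between children with and without first-degree T1DM relatives".

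**The concern.** The closing paragraph is where a reader looks to learn what the tables amount to. Read as written, it covers relatives, since their tables are among those it summarises. In relatives the printed power at 5% exposure is well below 80% on both primary end points, and for diabetes it is about a third or less.

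The relatives matter because secondary objective 2 concerns them directly. At 5% exposure and 2% yearly loss, printed power for diabetes is 0.82 in the general population (Table 6) and 0.27 in relatives (Table 7). Someone who trusted the summary could take a null result in relatives as informative when the analysis had little chance of detecting a hazard ratio of 2.0.

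**Working it through.** **Inputs.** Two-sided alpha is 0.01 with a log-rank test, so the critical value is 2.576 (section 10.3). On method, the protocol says "These calculations are based on the method of Lakatos". For relatives N = 788, with 13.3% conversion among the unexposed at 15 years for diabetes (Table 7) and at 6 years for autoantibodies (Table 10). On follow-up, "Thus all subjects will have 15 years of follow-up". The hazard ratio is 2.0.

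**Formula.** The unexposed hazard is λ0 = −ln(1 − 0.133)/15 = 0.00951 per year for diabetes, and λ1 = 2λ0. With exposed fraction p and loss rate η = −ln(1 − yearly loss):

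- At risk at time t: n1 = p·exp(−(λ1+η)t) and n0 = (1−p)·exp(−(λ0+η)t), with φ = n1/n0.
- Expected events in a short interval: d = N(λ0·n0 + λ1·n1)dt.
- z = Σ d[2φ/(1+2φ) − φ/(1+φ)] / √(Σ d·φ/(1+φ)²), summed over 15 years.
- Power = Φ(z − 2.576).

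**One cell in full.** Table 7, 5% exposed, no loss: 109 expected events, numerator 4.662, variance 4.881. So z = 4.662/√4.881 = 2.110 and power = Φ(−0.466) = 0.32. The printed value is 0.33.

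**Relatives at hazard ratio 2.0, printed and recomputed.**

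| Exposure, yearly loss | Table 7 printed | Recomputed | Table 10 printed | Recomputed |
|---|---|---|---|---|
| 5%, 0% | 0.33 | 0.32 | 0.67 | 0.68 |
| 5%, 2% | 0.27 | 0.27 | not readable in my copy | 0.61 |
| 10%, 0% | 0.62 | 0.61 | 0.94 | 0.94 |
| 10%, 2% | 0.53 | 0.53 | 0.89 | 0.90 |
| 10%, 5% | 0.42 | 0.43 | 0.80 | 0.82 |
| 10%, 10% | 0.29 | 0.30 | 0.65 | 0.68 |
| 20%, 0% | 0.87 | 0.86 | 0.99 | above 0.99 |
| 20%, 2% | 0.80 | 0.80 | 0.99 | 0.99 |

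The Table 7 cells agree to within 0.01, so the low values are not misprints. Reading the design as 5 years of staggered accrual plus 15 further years raises the two 5% diabetes cells only to 0.37 and 0.31, and the two 10% cells with 5% and 10% loss to 0.47 and 0.32.

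**Where the conclusion does hold** (printed, hazard ratio 2.0):

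| Table | 5% exposure, 0% / 2% loss | 10% exposure, 5% / 10% loss |
|---|---|---|
| 6, general population, diabetes | 0.89 / 0.82 | 0.95 / 0.83 |
| 8, pooled, diabetes | 0.98 / 0.96 | 0.99 / 0.96 |
| 9, general population, autoantibodies | 0.99 / 0.99 | 0.99 / 0.99 |
| 11, pooled, autoantibodies | 0.99 / 0.99 | 0.99 / 0.99 |

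The interim general-population tables for diabetes fall short at 5% exposure with 0% / 2% loss: 0.50 / 0.46 in Table 12 and 0.75 / 0.69 in Table 13.

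**What relatives can support at 80% power**, from the same formula:

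- Diabetes, hazard ratio 2.0: about 17% exposure with no loss, 20–21% with 2% loss and about 32% with 5% loss. With 10% loss it is not reached at any exposure (maximum about 0.66).
- Diabetes, detectable hazard ratio at 0% / 2% loss: 2.68 / 2.81 at 5% exposure and 2.22 / 2.32 at 10%.
- Autoantibodies, hazard ratio 2.0: about 10% exposure suffices with up to 5% loss.
- Autoantibodies, detectable hazard ratio at 5% exposure and 0% / 2% loss: 2.15 / 2.23.

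**The case against.** The relatives' power is printed in full in Tables 7 and 10, so nothing is hidden, and the authors may have had only the main analyses in mind. Recruitment is over, so no design decision turns on the sentence. All of that is fair and keeps this a matter of wording. It does not rescue a summary that says the tables show something two of them do not.

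Four stronger readings are tempting and should be resisted.

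- A reader might infer that the power statement in section 10.2 is false too. It is qualified as general and cites both enrolment targets, so it describes the pooled sample. Table 8 supports it there, with 0.96 to 0.99 at 10% exposure across all loss rates.
- A reader might take the 10% sentence as a promise of adequate power. It is worded as a minimum requirement. The most that can be said is that meeting it is not enough for diabetes in relatives.
- A reader might conclude that power in relatives is everywhere half or less of what is claimed. That fits some Table 7 cells only. For autoantibodies, the first primary outcome, 10% exposure gives 0.94, 0.89 and 0.80 at 0%, 2% and 5% loss.
- A reader might infer that objective 2 will be judged by comparing significance between the two groups. The protocol plans no such comparison. How the difference is to be tested is a separate analysis question that this correction does not need to settle.

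**Conclusion.** The concern stands in limited form. The 5% conclusion in section 10.3 is not true of relatives on either primary end point. Against the 80% yardstick, the printed shortfall for diabetes is 47 points with no loss (0.80 − 0.33) and 53 points with 2% loss (0.80 − 0.27). For autoantibodies with no loss it is 13 points (0.80 − 0.67). The 10% minimum for heavier loss is insufficient for diabetes in relatives, and for autoantibodies only at 10% yearly loss. This is a conclusion at odds with its own tables, with no arithmetic error in the relatives' tables.

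It rests on the planned 788 relatives, exponential conversion and the protocol's conversion rates. The protocol reports 8,677 children followed against 7,801 projected, without a split by family history. If relatives grew in proportion (788 × 8,677/7,801 ≈ 876), z at 5% exposure and 2% loss would rise from 1.968 to 1.968 × √(876/788) ≈ 2.075, giving power of about 0.31, so the conclusion would not change.

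That the sentence holds for the general population relies on Table 6 as printed. That table matches 5 years of accrual plus 15 further years. With exactly 15 years per child its cell at 5% exposure and 2% loss would be about 0.76 instead of 0.82.

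**What to change.** Leave section 10.2 as it is. In the closing paragraph of section 10.3, limit both sentences to the final general-population and pooled analyses. Naming the final analyses also excludes the interim results in Tables 12 and 13. Then add the relatives' power by end point, for example:

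- Relatives, diabetes: 80% power at a hazard ratio of 2.0 needs about 20% exposure with no more than 2% yearly loss. At 0–2% loss the detectable hazard ratio is about 2.7–2.8 at 5% exposure and 2.2–2.3 at 10%.
- Relatives, autoantibodies: about 10% exposure is enough at a hazard ratio of 2.0 with up to 5% yearly loss. At 0–2% loss the detectable hazard ratio at 5% exposure is about 2.1–2.2.

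The end-point labels are essential, because the 20% figure without its diabetes label would contradict Table 10. The cost is a few sentences of protocol text with no new data or analyses. The only downside is a less favourable stated power for relatives.
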